7.8.2 Laboratory data

No analyses are planned as safety laboratory test results will only be kept in the source data but not collected in the CRF (according to the CTP Section 5.2.3). Clinically relevant abnormal findings will be reported as AEs.

7.8.3 Vital signs

The analyses of vital signs (blood pressure and pulse rate) will be descriptive in nature. Descriptive statistics of vital signs over time and for the difference from baseline (see [Section 6.7](#)) will be provided.

Unscheduled measurements of vital signs will be assumed to be repeat measurements of the most recent scheduled measurement (e.g. for follow-up or confirmation of a particular value). Therefore, unscheduled measurements will be assigned to the planned time point of the previous scheduled measurement. However, for vital signs, descriptive statistics will be calculated by planned time point based on the last value of the subject at that planned time point (or assigned to that planned time point). If the time of measurement is missing for a scheduled post-baseline measurement, the scheduled measurement will be used in calculation of descriptive statistics (as time difference between scheduled and unscheduled cannot be assessed).

If the time of measurement is missing for an unscheduled measurement, this measurement will be listed but will be ignored for the calculation of descriptive statistics.

Clinically relevant findings in vital signs data will be reported as baseline conditions (prior to first administration of study treatment) or as AEs (after first administration of study treatment) if judged clinically relevant by the investigator, and will be analyzed as such.

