	13:03	[REDACTED] Questioning for AEs ¹ Vital Signs (BP, PR, SaO ₂) ¹	¹ [REDACTED], right before CANTAB RVP
5:06	13:06	CANTAB RVP	
	13:13	[REDACTED] Vital Signs (BP, PR, SaO ₂) ¹	[REDACTED], right before CANTAB SWM
	13:17	CANTAB SWM	
	13:23	[REDACTED] Vital Signs (BP, PR, SaO ₂) ¹	[REDACTED], right before CANTAB PAL
	13:27	CANTAB PAL	
	13:39	Questioning for AEs Vital Signs (BP, PR, SaO ₂)	
5:40	13:40	[REDACTED]	
	13:53	Vital Signs (BP, PR, SaO ₂)	
	13:54	[REDACTED]	
	13:57	[REDACTED]	
	14:00	Vital Signs (BP, PR, SaO ₂)	
	14:01	[REDACTED]	
	14:12	Vital Signs (BP, PR, SaO ₂)	
	14:13	[REDACTED]	
	14:19	Questioning for AEs Vital Signs (BP, PR, SaO ₂)	
6:20	14:20	[REDACTED]	
6:30 ¹	14:30 ¹	Vital signs (BP, PR, SaO ₂) [REDACTED] Stop of ketamine infusion¹ Stop of continuous ECG and SaO ₂ monitoring	¹ can be prolonged for a maximum of 15 min, in case delays from PT occur for CANTAB, [REDACTED] [REDACTED] or terminated earlier, if the above tests are completed (or any test drops out)
6:45	14:45	Vital Signs (BP, PR, SaO ₂)	
7:00	15:00	Questioning for AEs Vital Signs (BP, PR, SaO ₂) 12-lead ECG	
7:15	15:15	Vital Signs (BP, PR, SaO ₂)	
7:30 ¹	15:30 ¹	Questioning for AEs Vital Signs (BP, PR, SaO ₂) Confirmation of recovery from ketamine^{2,3} 240 mL fluid intake	¹ a minimum of 60 min of recovery follow up ² as per criteria of recovery from ketamine ³ lunch will be served after confirmation of recovery
8:00	16:00	[REDACTED]	
9:00	17:00	[REDACTED]	

Proprietary confidential information © 2021 Boehringer Ingelheim International GmbH or one or more of its affiliated companies

10:00	18:00	Questioning for AEs Vital Signs (BP, PR) 12-lead ECG	dinner will be served in the evening
24:00 ¹	08:00 ¹	Questioning for AEs Vital Signs 12-lead ECG Safety Laboratory (blood, urine) ^{2,3}	¹ Day 2 at V3, V4 and V5. The time is approximate; the procedures to be performed and completed \pm 2 h. ² Hematology, Biochemistry, Coagulation, Urinalysis ³ breakfast will be served after blood sampling
27:00 ¹	11:00 ¹	Questioning for AEs Vital Signs C-SSRS 'since last visit' DSST, MOAA/S, CADSS, SFST Targeted Physical Examination ² Discharge from trial site³	¹ time is approximate; the procedures to be performed and completed within 2 h prior to discharge ² incl. skin inspection for signs of rash, check for lymphadenopathy and neurological examination ³ after confirmation of fitness by the investigator, and at least 24h after the last study drug administration

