5.2.2 Vital signs

Systolic and diastolic blood pressures (BP) as well as pulse rate (PR) will be measured by a blood pressure monitor (e.g. Dinamap Pro 100, [REDACTED] or comparable) at the times indicated in the [Flow Chart](#), after subjects have rested for at least 5 min in a supine position when possible.

Pulse oximetry is a non-invasive method for monitoring O₂ saturation (SaO₂). A blood-oxygen monitor displays the percentage of blood that is loaded with oxygen and used to

Proprietary confidential information © 2021 Boehringer Ingelheim International GmbH or one or more of its affiliated companies

detect abnormalities in ventilation. SaO_2 will be measured by a pulse oximeter (e.g. [REDACTED]
[REDACTED] TruSat, [REDACTED] or comparable).

All recordings should be made using the same type of blood pressure and oxygen saturation recording instrument on the same arm, if possible.

At the screening examination (Visit 1), orthostatic tests will be performed. Subjects should have spent at least 5 min in the supine position before blood pressure and pulse rate will be measured the first time. Further 2 measurements will be performed immediately after standing up and after 3 min in a standing position.

At the screening ketamine challenge (Visit 2) and on treatment days (Visits 3, 4 and 5):

- Before ketamine infusion and after confirmation of recovery from ketamine, vital signs (BP, PR, SaO_2) to be measured at the time points indicated in the [Flow Chart C](#) and [Flow Chart D](#). Vital signs 5 min prior to start of ketamine infusion (incl. recording of respiratory rate and effort this time) will serve as baseline for confirmation of recovery from ketamine.*
- During ketamine infusion, vital signs (BP, PR, SaO_2) to be measured and recorded in the breaks between the tests at the time points indicated in the [Flow Chart C](#) and [Flow Chart D](#). Oxygen saturation (SaO_2) will be monitored continuously from start of ketamine infusion until confirmation of recovery from ketamine (see below). If SaO_2 is <90%, a prompt medical evaluation is to be done.*

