6. GENERAL ANALYSIS DEFINITIONS

6.1 TREATMENTS

For basic study information on treatments to be administered, assignment of treatment groups, and selection of doses, cf. Section 4 of the CTP.

Each subject is planned to be treated in three subsequent treatment periods with one single dose at Day 1 in each treatment period:

- Test treatment 1 (T1):
300 mg of Lamotrigine as tablet
- Test treatment 2 (T2):
[REDACTED] of BI 409306 as film-coated tablet
- Test treatment 3 (T3):
[REDACTED] of BI 425809 as film-coated tablet
- Reference treatment (R):
Placebo as film-coated tablet

Each subject is planned to be randomly allocated to one of 18 3-period sequences including placebo in one of the periods and 2 out of 3 active treatments in the remaining periods:

T1–T2–R, T1–R–T2, T1–T3–R, T1–R–T3, T2–T1–R, T2–R–T1, T2–T3–R, T2–R–T3, T3–R–T1, T3–T1–R, T3–T2–R, T3–R–T2, R–T1–T2, R–T2–T1, R–T1–T3, R–T3–T1, R–T2–T3, R–T3–T2.

Each treatment period is separated by a washout period of at least 11 days.

[REDACTED] : *The Residual Effect Period (REP)* [REDACTED]
[REDACTED], for lamotrigine 10 days, and for ketamine 24 hours. This is the period
after the last dose with measurable drug levels and/or pharmacodynamic effects is still likely
to be present.

For statistical analyses of AEs and vital signs, the following separate analysis phases will be defined for each subject:

Table 6.1: 1 Analysis phases for statistical analysis of AEs and actual treatment for analysis of vital signs

Study analysis phase	Label of analysing treatment	Label of actual treatment	Start	End
Screening	Screening	Screening	Date of informed consent	Start date/time of screening ketamine infusion
		Screening+Ketamine	Start date/time of screening ketamine infusion	End date/time of screening ketamine infusion + 24 h
		Screening	End date/time of screening ketamine infusion + 24 h	Start date/time of first administration of study treatment (Planned time: 00:00h) in the respective treatment period
On treatment ^{1, 2, 3}	Placebo, [REDACTED] BI 409306, BI 425809 or 300mg Lamotrigine, respectively	Placebo, [REDACTED] BI 409306, BI 425809 or 300mg Lamotrigine, respectively	Start date/time of administration of the first study treatment (Planned time: 00:00h) in the respective treatment period	Start date/time of on-treatment ketamine infusion or 12:00 a.m. on day after subject's trial completion date, whatever comes first

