	Placebo+Ketamine, [REDACTED] BI 409306+Ketamine, [REDACTED] BI 425809+Ketamine or 300mg Lamotrigine+Ketamine, respectively	Start date/time of on-treatment ketamine infusion	End date/time of on-treatment ketamine infusion + 24 h or 12:00 a.m. on day after subject's trial completion date, whatever comes first	
	Placebo, [REDACTED] BI 409306, BI 425809 or 300mg Lamotrigine, respectively	End date/time of on-treatment ketamine infusion + 24 h	Start date/time of administration of the second study treatment (Planned time: 03:00h) in the respective treatment period + 11 days * 24 h/day (for BI 409306, BI 425809, lamotrigine and placebo) or Date/time of administration of study drug in the next treatment period or 12:00 a.m. on day after subject's trial completion date, whatever comes first	
Follow-up	F/U Placebo, F/U [REDACTED] BI 409306, F/U [REDACTED] BI 425809 or F/U 300mg Lamotrigine, respectively	F/U Placebo, F/U [REDACTED] BI 409306, F/U [REDACTED] BI 425809 or F/U 300mg Lamotrigine, respectively	Start date/time of administration of the second study treatment (Planned time: 03:00h) in the respective treatment period + 11 days * 24 h/day (for BI 409306, BI 425809, lamotrigine and placebo)	Date/time of administration of the respective treatment in the next treatment period, if applicable, or 12:00 a.m. on day after subject's trial completion date, whatever comes first.

¹ See [Section 6.7](#) for definition of baseline, which will be used in the statistical analyses of vital signs.

² A REP of 11 days will be used for all study treatments (BI 409306, BI 425809, lamotrigine and placebo) to avoid any bias which might occur due to different observation times. This may lead to an overestimation of AEs in the treatment periods in which subjects received a study treatment with considerably lower REP.

³ The on-treatment phase extends from Day 1 00:00h (planned time) to Day 11 03:00h (planned time) to include AEs which occur after the start of the first study drug (or corresponding placebo) administration (which is not necessarily the analysing treatment of the respective treatment period) as well as AEs which occur within the REP of the second study drug (or corresponding placebo).

Analysis phases for statistical analysis of AEs are defined for each subject as described in [Table 6.1: 1](#).

AE summary tables will present results for the on-treatment phase only. All AEs will be listed.

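### SAP 7.8.3 carries timed unscheduled BP and pulse readings back across a dose or the ketamine start, so a few post-event values can appear in pre-event rows of the descriptive table

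*SAP*

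**What the plan says.** SAP 7.8.3 gives the reason for its rule: "Unscheduled measurements of vital signs will be assumed to be repeat measurements of the most recent scheduled measurement". It follows that "unscheduled measurements will be assigned to the planned time point of the previous scheduled measurement". The summary at each planned time is then "based on the last value of the subject at that planned time point (or assigned to that planned time point"), so a reassigned reading displaces the scheduled one.

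Two exceptions are stated. An unscheduled reading without a recorded time is set aside: "this measurement will be listed but will be ignored for the calculation of descriptive statistics". If a scheduled post-baseline reading has no time, the scheduled reading is kept. Neither exception concerns dosing.

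SAP 6.1 works by actual time. Its Table 6.1: 1 ("Analysis phases for statistical analysis of AEs and actual treatment for analysis of vital signs") moves a subject from the drug label to the drug+Ketamine label at "Start date/time of on-treatment ketamine infusion". Vital signs listings carry that label as an extra column. The same section treats a measurement as on-treatment according to when it was taken, and asks for baseline and post-baseline values to be kept clearly apart. SAP 6.7 sets the safety baseline as the last value available before the treatment concerned is given.

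In Flow Chart D, the first BP and pulse reading on ketamine is at 13:03, described as "right before CANTAB RVP" (13:06).

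**The concern.** Treating an extra reading as a confirmation of the last scheduled one is sensible while nothing has happened in between. It is not sensible once a drug has been given. The reading is then taken under a different condition, and the table shows it at a time when the subject had not yet received the drug or the ketamine.

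BP and pulse are the vital signs that the SAP summarises numerically. SaO2 and laboratory results stay in source data, and ECG gets no separate analysis. Protocol 1.2.4.3 lists rises in blood pressure and heart rate as common with ketamine. Protocol 1.4 says that neither BI compound has been given with ketamine before. The minutes around dosing and the bolus are therefore where a misplaced reading would matter most to someone reading the table.

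The SAP also disagrees with itself: the listing and the table can place the same reading on opposite sides of the ketamine start.

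**Working it through.** The plan gives no figure to reproduce. The check applies the SAP 7.8.3 rule to the Flow Chart D clock.

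**Step 1: inputs.** Visible BP and pulse times on Day 1 are 06:00 (approximate), 09:00, 12:00, 12:55, 13:03, 13:13 and later. Dose 1 is at 08:00, dose 2 at 11:00 and ketamine start at 13:00. The bolus takes 1 minute and ends at 13:01.

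**Step 2: gap after each event.** Gap = next scheduled reading minus event time.

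| Event | Previous scheduled | Next scheduled | Gap | Row that receives a timed unscheduled reading |
|---|---|---|---|---|
| Dose 1, 08:00 | 06:00 | 09:00 | 60 min | -2:00 (pre-dose) |
| Dose 2, 11:00 | 09:00 (last visible) | 12:00 (next visible) | up to 60 min | a row before dose 2 |
| Ketamine start, 13:00 | 12:55 | 13:03 | 3 min | 4:55 (pre-ketamine) |

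Entries around dose 2 are partly redacted. If one of them holds a BP and pulse reading, the receiving row could be later than 1:00 or the gap shorter than 60 minutes. A reading before the next scheduled one would still cross the dose.

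**Step 3: how far the ketamine gap can stretch.** From the end of the bolus, 13:03 - 13:01 = 2 min. If the reading is taken just before the 13:06 test, the gap is 5 min. If the 13:03 reading is missed, it runs to 13:13, or 12 min. As shares of the 89-minute infusion after the bolus, these are 2/89 = 2%, 5/89 = 6% and 12/89 = 13%. After that, unscheduled readings fall on on-ketamine rows.

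**Step 4: one reading, two places.** Take a timed unscheduled reading at 13:02.
- Under Table 6.1: 1 it is drug+Ketamine, because it follows the actual start of the infusion.
- Under 7.8.3 it is summarised at 4:55 and replaces the pre-ketamine value.

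For a reading at 08:30, SAP 6.7 keeps the true pre-dose value as baseline, while 7.8.3 puts the post-dose value in the -2:00 row. That row then no longer matches the baseline used for the differences.

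**Step 5: size in a row mean (assumed values).** The documents do not say how many such readings there are or how large. If k of n subjects have a row value replaced by one d mmHg higher, the mean moves by k x d / n.
- Active treatment, n = 24: from 1 x 10/24 = 0.4 to 3 x 30/24 = 3.8 mmHg.
- Placebo, n = 36: from 1 x 10/36 = 0.3 to 3 x 30/36 = 2.5 mmHg.

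**Step 6: after the fix.** With a stop at each administration and at ketamine start, all three gaps become 0 min.

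**The case against.** The strongest reply is that little depends on these rows. The analysis is descriptive, clinically relevant findings become adverse events, the listings keep the actual phase, and the Report Planning Meeting can rule on discrepant values. SAP 6.1 already separates baseline from post-baseline, and it refers technical detail to an ADS Plan that is not among the documents. All of this limits the consequences. None of it corrects the table: a properly timed reading is not a discrepant value, and 7.8.3 as written still places it in the wrong row.

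Four stronger readings are tempting, and the documents do not support them.

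- **The ketamine-related rise would be understated.** Assume 125 mmHg at 4:55, 165 unscheduled at 5:02 and 160 at 13:03. Subtracting the table rows gives 160 - 165 = -5 instead of 160 - 125 = +35. The SAP plans no such subtraction. Its difference at 13:03 is taken from the pre-dose baseline of SAP 6.7, and the 160 stays in its own row. Only the 4:55 row, including any difference shown there, is altered.
- **The 4:55 reading is the baseline.** Protocol 5.2.2 does say "Vital signs 5 min prior to start of ketamine infusion (incl. recording of respiratory rate and effort this time) will serve as baseline", but for confirming recovery from ketamine. It is not the baseline of the statistical analysis.
- **All readings after the bolus are tabulated as pre-ketamine.** This holds only until the 13:03 reading.
- **Every unscheduled reading in three fixed windows is misplaced.** Untimed ones are excluded, and the dose-2 window rests on partly redacted rows.

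**Conclusion.** The rule is wrong as written, with a narrow effect. It can put post-dose or on-ketamine values into rows that a reader will take as pre-dose or pre-ketamine, and it conflicts with the actual-time phases in SAP 6.1. On the planned schedule the exposure is 60 minutes after dose 1, up to 60 minutes after dose 2 and 3 minutes after ketamine start.

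Only the by-planned-time descriptive rows for BP and pulse are affected. The SAP 6.7 baseline, change from baseline at scheduled on-ketamine times, the scheduled 13:03 value, the listings, adverse events, and the primary and secondary endpoints are not.

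The conclusion assumes that the visible Flow Chart D times are the scheduled ones and that the ADS Plan does not already restrict the rule. The mmHg shifts above are illustrations. The actual shift could be zero if no such reading was taken.

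**What to change.** Amend SAP 7.8.3 along these lines: an unscheduled vital signs reading is assigned to the previous planned time only if, by actual date/time, no study-drug administration and no start of the ketamine infusion lies between the two. Otherwise it is left out of the by-planned-time statistics and listed under its actual treatment phase.

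The times needed are already in Table 6.1: 1. That table does not open a new phase at dose 2, so the condition must also use the second-administration time, which the table already cites for the end of the on-treatment phase.

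The cost is one sentence and one programming condition, with no new data. The drawback is that the few readings concerned drop out of the summary table. If the sponsor wants them summarised, a separate row by actual phase could be added, but it would hold only sporadic values and be hard to interpret.

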7.8.4 ECG

Abnormal findings in ECG will be reported as baseline conditions (at screening) or as AEs (during the trial) if judged clinically relevant by the investigator, and will be analyzed as such. No separate listing or analysis of ECG data will be prepared.

7.8.5 Others

7.8.5.1 Physical examination

Physical examination findings will be reported as relevant medical history/baseline condition (if a condition already exists before first administration of study treatment) or as AE (if condition emerges after first administration of study treatment) and will be summarized as such. No separate listing or analysis of physical examination findings will be prepared.

7.8.5.2 Body weight

Body weight will only be listed.

7.8.5.3 Suicidality assessment

Suicidality monitoring will be performed as described in Section 5.2.5.2 of the CTP, results will be listed. Additionally, the frequency of subjects categorized by any question answered with 'Yes' (or all answered with 'No' or missing) will be presented. Results for subjects who answered any question with 'Yes' will additionally be listed. Findings will also be reported as AEs.

[REDACTED]

[REDACTED]

[REDACTED]

[REDACTED]

7.8.5.5 Visual acuity test

The visual acuity test will be performed as described in Section 5.2.5.4 of the CTP. Any deterioration occurring during the study will be documented as an AE.

[REDACTED]

[REDACTED]

[REDACTED]

[REDACTED]

[REDACTED]

[REDACTED]

8. TIMEPOINT OF RELEASE OF TREATMENT INFORMATION

The treatment information will be loaded into the trial database after completion of enrollment, i.e. the randomization has completed.

11. HISTORY TABLE

Table 11: 1 History table

Version	Date (DD-MMM- YY)	Author	Sections changed	Brief description of change
Final	14-Oct-2022	[REDACTED]	None	First final TSAP version
